4.4.2 Prohibited Medications/Treatments

The decision to administer a prohibited medication/treatment will be made with the safety of the study participant as the primary consideration. When possible, the Sponsor or Sponsor's representative should be notified before a prohibited medication/treatment is administered.

Subjects must not be enrolled in another study and may not receive another investigational product during the course of this study.

Prior to attending study visits, subjects must not apply facial cosmetics.

For information regarding medications/treatments requiring washout prior to treatment, see *Section 6.1.3: Washout of Prohibited Medications/Treatments*.

4.4.2.1 Anticoagulant Medications

Subjects on a regimen of anticoagulation therapy (eg, warfarin, clopidogrel) should not be enrolled in this study. NSAID use is permitted to improve patient comfort during BELKYRA® treatment.

Subjects who receive VOLUMA™ and who are taking NSAIDs must be warned of the potential increased risk of bleeding and hematomas during injection.

Use, discontinuation and resumption, as applicable, of anticoagulant medication will be recorded as concomitant medication.

4.4.2.2 Facial Procedures/Treatments

During the study, subjects must not:

- Receive permanent facial implants (eg, polymethylmethacrylate, silicone, polytetrafluoroethylene) anywhere in the face or neck
- Undergo fat injections in the malar, chin, or jawline area
- Undergo any piercing or tattooing procedures below the subnasale
- Undergo semi-permanent dermal fillers (eg, calcium hydroxylapatite, L-poly lactic acid) below the subnasale
- Undergo mesotherapy or cosmetic treatment (laser, photomodulation, intense pulsed light, radio frequency, dermabrasion, moderate or greater depth chemical peel, liposuction, lipolysis, or other ablative procedures) anywhere in the face or neck
- Receive botulinum toxin injections in the chin, masseter, periorial area, or platysmal bands

Clinical Study Protocol: CMO-MA-FAS-0513

4.4.2.3 Special Diet or Activities

Within the first 24 hours after filler treatment with VOLUMA™, at Visit 4, and if a Touch-up treatment is performed at Visit 5, subjects should avoid strenuous exercise, extensive sun or heat exposure and alcoholic beverages. Exposure to any of the above may cause temporary redness, swelling, and/or itching at the injection sites.

4.4.2.4 Weight Loss Medications

Subject should not be prescribed medication with the purpose of inducing weight loss during the course of the study. Additionally, subjects should not be prescribed other medications for which significant weight loss is a known common side effect without consulting with the Sponsor.

5 TREATMENT

5.1 INVESTIGATIONAL PRODUCT

Commercial grade product will be provided by Allergan for use in this study. The product will be labeled as investigational and shall be used only for subjects enrolled in this trial, at no cost to the subject, in accordance with the conditions specified in the protocol. Commercial grade product obtained by any other method shall not be used for subjects in this study. Allergan will provide each study site with sufficient study treatment/devices for all study subjects.

5.1.1 BELKYRA®

BELKYRA® is a clear, colorless, sterile solution supplied in 2 mL vials, 4 vials in each kit. The vials are intended for single subject use. Each milliliter of the solution contains 10 mg of deoxycholic acid.

BELKYRA® is injected into subcutaneous fat tissue in the submental area using an area-adjusted dose of 2 mg/cm².

- A single treatment consists of up to a maximum of 50 injections, 0.2 mL each (up to a total of 10 mL), and injected 1 cm apart.
- Up to 6 single treatments may be administered at intervals no less than 8 weeks apart.

BELKYRA® should be administered by a licensed healthcare professional.

5.1.2 VOLUMA™

VOLUMA™ injectable gel is a sterile, biodegradable, non-pyrogenic, viscoelastic, clear, colorless, homogeneous gel implant. It consists of cross-linked HA produced by *Streptococcus* species of bacteria, formulated to a concentration of 20 mg/mL, and 0.3% lidocaine in a physiological buffer. VOLUMA™ injectable gel is supplied in 1 mL syringes, 2 syringes per kit. The maximum total volume allowed for an individual subject for the initial and touch-up treatments combined during the study is 6 mL (3 mL per side).

Clinical Study Protocol: CMO-MA-FAS-0513

5.1.3 Blinding and Randomization

This is an open-label, single-arm study. Thus, blinding and randomization methods will not be implemented.

5.1.4 Treatment Assignment

Sequentially numbered investigational product (IP) will be provided to each investigative site. IP will be assigned sequentially to eligible subjects beginning with the lowest numbered unassigned IP at the site. Each kit will be assigned to one subject. Unopened vials/syringes in an assigned kit may be used for subsequent treatments for the assigned subject. Kits shall not be shared between subjects.

The assigned IP will be labelled with the subject's initials, subject's study number and date of assignment. The IP number(s) assigned to a specific subject will be recorded in that subject's source document and on the site's inventory list as described in *Section 5.2.1: Storage*.

BELKYRA® will be provided in kits containing 4 vials, each vial containing 2 mL of product. Each kit will be labeled as investigational product and will be sequentially numbered. A maximum of 5 vials (10 mL) may be used per treatment. Partially used vials/kits shall not be shared between individuals.

VOLUMA™ will be provided in kits containing 2 syringes, each syringe containing 1 mL of product. Each kit will be labeled as investigational product and will be sequentially numbered. The maximum of 3 kits (total volume 6 mL) is allowed per subject for the initial and touch-up treatments combined. Partially used syringes/kits shall not be shared between individuals.

5.2 STORAGE, HANDLING AND DESTRUCTION

5.2.1 Storage

All study drug/devices must be stored in a locked, secure area accessible only to study personnel. The study site shall keep an inventory of all kits received, used and not used. The disposition of each vial/syringe contained in the kit will also be inventoried.

5.2.1.1 BELKYRA®

The vials of BELKYRA® should be stored at room temperature in a locked, limited-access storage area.

5.2.1.2 VOLUMA™

VOLUMA™ is to be stored at room temperature in a locked, limited-access storage area.

5.2.2 Handling

5.2.2.1 BELKYRA®

BELKYRA® is clear, colorless and free of particulate matter. BELKYRA® vials should be visually inspected for particulate matter and/or discoloration. If the solution is discolored

Clinical Study Protocol: CMO-MA-FAS-0513

and/or contains particulate matter, the vial is to be labeled as “DAMAGED” and a new vial obtained for the subject. Document the reason the original vial was considered damaged. Record the vial number for the damaged vial and the vial number for the replacement vial that was used. Used, partially used or damaged vials should be handled per *Section 5.2.3 Destruction*.

Detailed instructions for BELKYRA® handling are in the *BELKYRA® Summary of Product Characteristics*.

5.2.2.2 VOLUMA™

VOLUMA™ is an injectable gel with a clear appearance. If a syringe contains material that is not clear, do not use the syringe. If either one or both syringes in a kit is defective (e.g., gel is not clear, plunger does not work, etc.), the entire kit is considered damaged. Label the kit as “DAMAGED” and obtain a new kit for the subject. Document the reason the original kit was considered damaged. Record the kit number for the damaged kit and the kit number for the replacement kit that was used. All syringes (unused, partially-used or used) should be returned to the kit. Used, partially used or damaged kits should be handled per *Section 5.2.3 Destruction*.

Detailed instructions for VOLUMA™ handling are provided in the *JUVÉDERM® VOLUMA™ WITH LIDOCAINE Directions for Use (Appendix 2)*.

5.2.3 Destruction

All vials/kits shall be retained in a secure location for audit by the Sponsor. Partially-used and unused kits will be shipped for destruction by the site monitor. Used kits shall be destroyed at the site following local site practices and regulations after the kit has been audited by the site monitor.

5.3 TREATMENT ADMINISTRATION

5.3.1 BELKYRA®

The safe and effective use of BELKYRA® depends on the use of the correct number and locations for injections, proper needle placement, and administration techniques. A brief summary of the method of use is provided below; full details of treatment administration will be provided in *Appendix 1: BELKYRA® Product Information*.

BELKYRA® is injected into subcutaneous fat tissue in the submental area using an area-adjusted dose of 2 mg/cm². The Investigator will determine the appropriate area of submental tissue to be treated.

- A single treatment consists of up to a maximum of 50 injections, 0.2 mL each (up to a total of 10 mL), and injected 1 cm apart.
- Up to 6 single treatments may be administered at intervals no less than 8 weeks apart.

The planned treatment area should be outlined with a surgical pen and a 1 cm injection grid applied to mark the injection sites. Injections near the area of the marginal mandibular nerve

Clinical Study Protocol: CMO-MA-FAS-0513

should be avoided. Similarly, injection into the platysma should also be avoided. BELKYRA® should not be injected outside the defined parameters.

- Using a large bore needle, draw 1 mL of BELKYRA® into a sterile 1 mL syringe and expel any air bubbles in the syringe barrel.
- Have the subject tense the platysma. Pinch the submental fat and, using a 30 gauge (or smaller) 0.5-inch needle, inject 0.2 mL of BELKYRA® into the pre-platysmal fat next to each of the marked injection sites by advancing the needle perpendicular to the skin.
- Injections that are too superficial (into the dermis) may result in skin ulceration. Do not withdraw the needle from the subcutaneous fat during injection as this could increase the risk of intradermal exposure and potential skin ulceration.
- Avoid injecting into the post-platysmal fat by injecting BELKYRA® into fat tissue at the depth of approximately mid-way into the subcutaneous fat layer.
- If at any time resistance is met as the needle is inserted, indicating the possibility of contact with fascial or nonfat tissue, the needle must be withdrawn to an appropriate depth before the injection is administered.
- Avoid injecting into other tissues such as the muscle, salivary glands and lymph nodes.
- Upon needle withdrawal, pressure may be applied to each injection site as necessary to minimize bleeding; an adhesive dressing may be applied.

For information on use of local anesthesia and use of rescue medications, refer to *Section 4.4.1.1: Anesthesia* and *Section 4.4.1.2: Rescue Medications*, respectively. For information on prohibited medications/treatments refer to *Section 4.4.2: Prohibited Medications/Treatments*.

5.3.2 VOLUMA™

[figure not shown]
The Investigator will determine the appropriate volume of VOLUMA™ to be injected for restoring volume along the mandibular border and enhancement of the overall contour of the jawline. Two weeks following the initial VOLUMA™ treatment (Visit 4), touch up treatment may be administered at Visit 5. The maximum total volume allowed for an individual subject for the initial and touch-up treatments combined is 6 mL (3 mL per side).

A brief summary of the method of use is provided below; full details for the injection of VOLUMA™ will be provided in *Appendix 2: Juvéderm® VOLUMA™ with Lidocaine Directions For Use*.

Use of needle or cannula for the procedure is per investigator judgement. If the Investigator opts to use a cannula for the procedure, the specific cannula to be used will be per Allergan guidance.

- Prior to the injection, the area to be treated should be disinfected thoroughly.
- Confirm that the product flows out of the needle or cannula upon depressing the plunger rod.

Clinical Study Protocol: CMO-MA-FAS-0513

6.1.4 Subject Enrollment

An individual who provides written informed will be assigned a subject number and will undergo screening for participation. Subjects who meet eligibility criteria (See Section 4.2 and 4.3) will receive BELKYRA® treatment. Subjects who meet eligibility criteria and consent to participate in the Biopsy Sub-study will have a biopsy sample collected prior to the treatment with BELKYRA®.

Eligible subjects who withdraw after undergoing biopsy and before receiving BELKYRA® treatment may be replaced by another suitable subject in order that 50 subjects are treated with BELKYRA® and are included in the Full Analysis Set for analysis (see Section 10.1.1). The subject number will not be reassigned to a different subject. Subjects who have received BELKYRA® treatment will not be replaced.

■ [REDACTED]

[REDACTED]

[REDACTED]

[REDACTED]

[REDACTED]

■ [REDACTED]

[REDACTED]

[REDACTED]

[REDACTED].

Clinical Study Protocol: CMO-MA-FAS-0513

[REDACTED]

[REDACTED]

[REDACTED]

[REDACTED]

[REDACTED]

[REDACTED]

[REDACTED]

[REDACTED]

Clinical Study Protocol: CMO-MA-FAS-0513

[REDACTED]

[REDACTED]

[REDACTED]

[REDACTED]

[REDACTED]

[REDACTED]

[REDACTED]

[REDACTED]

[REDACTED]

[REDACTED]

[REDACTED]

Clinical Study Protocol: CMO-MA-FAS-0513

[REDACTED]

[REDACTED]

[REDACTED]

- [REDACTED]
- [REDACTED]
- [REDACTED]
- [REDACTED]

[REDACTED]

[REDACTED]

[REDACTED]

[REDACTED]

[REDACTED]

[REDACTED]

[REDACTED]

[REDACTED]

[REDACTED]

- [REDACTED]
- [REDACTED]
- [REDACTED]
- [REDACTED]

[REDACTED]

[REDACTED]

[REDACTED]

[REDACTED]

[REDACTED]

- [REDACTED]
- [REDACTED]
- [REDACTED]
- [REDACTED]

Clinical Study Protocol: CMO-MA-FAS-0513

• [REDACTED]

[REDACTED]
[REDACTED]
[REDACTED]
[REDACTED]
[REDACTED]
[REDACTED]

[REDACTED]
[REDACTED]
[REDACTED]
[REDACTED]

[REDACTED]
[REDACTED]
[REDACTED]
[REDACTED]

[REDACTED]

[REDACTED]
[REDACTED]
[REDACTED]
[REDACTED]
[REDACTED]

[REDACTED]
[REDACTED]

[REDACTED]
[REDACTED]
[REDACTED]
[REDACTED]
[REDACTED]
[REDACTED]
[REDACTED]
[REDACTED]
[REDACTED]
[REDACTED]
[REDACTED]

Clinical Study Protocol: CMO-MA-FAS-0513

[REDACTED]

[REDACTED]

[REDACTED]

[REDACTED]

[REDACTED]

[REDACTED]

Clinical Study Protocol: CMO-MA-FAS-0513

6.3.3 VOLUMA™ Treatment Period

During the VOLUMA™ treatment period (Visits 4 to 6), subjects will additionally be instructed to:

- Within the first 24 hours after study treatment, avoid strenuous exercise, extensive sun or heat exposure, and alcoholic beverages.
- Complete the ISR Diary: every day, one page per day, around the same time of the day as the treatment.
- Bring the ISR Diary to the next study visit.

7 METHODS OF ASSESSMENT AND ENDPOINTS

7.1 STUDY PROCEDURES

7.1.1 Demographic Data

Subject demographic data will be collected at the Screening Visit.

These data include date of birth, age, gender, race, and ethnicity. Height and weight measurements will also be collected for use in calculating BMI.

7.1.2 Medical History

Medical history will be obtained from each subject at the Screening Visit.

Medical history includes pertinent surgical history and a detailed history of prior facial aesthetic procedures with start and stop dates, if applicable, as well as any discontinuations due to intolerability or toxicity.

7.1.3 Concomitant Medications/Procedures

Concomitant medication/procedure status shall be collected at all visits. Concomitant medications include prescription medications, dietary supplements, over-the-counter medications, and oral herbal preparations.

A list of concomitant medications/procedures will be collected at the Screening visit. Data collected shall be medication/treatment name, dose, frequency, start date, stop date (if applicable). All medications or treatments received within 4 weeks before the Screening visit shall be recorded. Medications/procedures received more than 4 weeks before Screening and in the Investigator's judgment is pertinent to this study, should also be recorded.

Following treatment at Day 0, subjects will be asked at each subsequent study visit whether any new medication/procedures have been administered or if any changes in dosage or frequency, have occurred since the previous visit. All concomitant medications and procedures will be recorded on eCRFs.

Clinical Study Protocol: CMO-MA-FAS-0513

7.1.4 Fitzpatrick Skin Type

The subject's Fitzpatrick skin type will be determined at the Screening visit using the parameters listed in *Appendix 12*.

7.1.5 Urine Pregnancy Test

The urine pregnancy test will be performed at the Screening visit and prior to administration of any study treatment. The urine pregnancy test will be performed only for women of childbearing potential. The woman's childbearing status must be clearly reported in the source documentation.

The pregnancy test will be performed by urine dipstick. Positive pregnancy test results must be repeated to confirm the result. Women of childbearing potential must have a negative pregnancy test before any study treatments are given.

7.1.6 Photographic Imaging

Standardized facial photographic images will be captured prior to each study treatment and within 60 minutes of VOLUMA treatment. Equipment and training for the capturing of images will be provided by a vendor selected by Allergan. Captured images will be transferred to the imaging vendor for archiving. Instructions for image capture, transmission and central assessment will be contained in the procedure manual.

7.1.7 Biopsy

Subjects who consent to participate in the optional Biopsy Sub-study will have a biopsy sample collected at least 4 weeks prior to the first BELKYRA® treatment at Visit B1. Biopsy sample collection may occur on the same day as Screening (Visit 1) if all eligibility criteria are confirmed prior to performing the biopsy. A second biopsy sample will be collected 8 weeks following the last BELKYRA® treatment at Visit B2. When the second biopsy lesion is healed (at least 4 weeks), VOLUMA™ treatment may occur (see Figure 3.1).

Biopsy samples, approximately 2 mm, will be excised from the submental area approximately 1.5 cm left and right of midline (baseline and post-treatment, respectively). Biopsy samples will be transferred to 10% neutral buffered formalin and shipped to a central laboratory for histopathology.

Additional details on biopsy logistics (e.g. sample collection, fixative, shipping) will be available in the Biopsy Manual.

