3 STUDY DESIGN

This Phase IV trial is a prospective, open-label, multi-center, interventional, drug and medical device, post-marketing study. Each subject will act as his/her own control. Subjects will attend a minimum of 6 and maximum of 18 visits (see *Figure 3.1*)

Clinical Study Protocol: CMO-MA-FAS-0513

Approximately 50 subjects will be enrolled. Approximately 10 subjects are expected to participate in the Biopsy Sub-study.

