4 STUDY POPULATION AND ENTRY CRITERIA

4.1 NUMBER OF SUBJECTS

Approximately 50 subjects will be treated in this study. Approximately 10 subjects will participate in the Biopsy Sub-study. Subjects who discontinue after receiving treatment on Day 0 will not be replaced.

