6.2.3.2 Biopsy Sub-study

Subjects who consent to participate in the optional Biopsy Sub-study will have a biopsy sample collected at least 4 weeks prior to the first BELKYRA treatment at Visit B1. A second biopsy sample will be collected 8 weeks following the last BELKYRA treatment at Visit B2. Biopsy samples, approximately 2 mm, will be excised from the submental area approximately 1.5 cm from the submental crease and 1.5 cm left and right of midline.

- Objective: Evaluate changes from baseline to last BELKYRA® treatment based on histological evaluation of the submental tissue biopsies.
- Analysis: For each biopsy sample, mean levels of pro-collagen I, collagen I, collagen III, and elastin will be evaluated. For each subject, changes in expression from baseline to after final BELKYRA® treatment will be calculated for each marker. The mean change across all subjects for each marker will be determined. Statistical comparisons from baseline to after final BELKYRA® treatment (based on mean change) may be performed to determine the significance of these observations.

Refer to Appendix I for Analysis Plan of Biopsy Data

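### Every baseline biopsy is taken on the left and every post-treatment biopsy on the right, so a systematic side difference could not be told apart from a BELKYRA effect

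*Protocol*

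**What the plan says.** Protocol 7.1.7 (Biopsy) gives the two sampling sites as "approximately 1.5 cm left and right of midline (baseline and post-treatment, respectively"). The last word ties left to the baseline sample and right to the post-treatment sample, for all sub-study subjects. SAP 6.2.3.2 gives the sites as "approximately 1.5 cm from the submental crease and 1.5 cm left and right of midline" and does not link side to visit.

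The analysis in SAP 6.2.3.2 covers pro-collagen I, collagen I, collagen III and elastin. "For each subject, changes in expression from baseline to after final BELKYRA® treatment will be calculated for each marker", and then "The mean change across all subjects for each marker will be determined". On inference the SAP says only that comparisons "may be performed to determine the significance of these observations". The visible text names no test, significance level or sidedness.

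On size and control, Protocol 4.1 says "Approximately 10 subjects will participate in the Biopsy Sub-study", and Protocol 3 says "Each subject will act as his/her own control". Protocol 5.1.3 confirms a single arm. No untreated pair of biopsies is planned.

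The two documents rank the endpoint differently. Protocol 2.1.2 lists histological change as a secondary objective. The SAP introduction calls it exploratory, and SAP 2.3 leaves it out of the secondary objectives.

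**The concern.** Each subject's change is post-treatment minus baseline. Under the fixed order it is also right minus left. If a marker tends to be higher on one side in this population, that tendency appears as a treatment effect of the same size. Nothing in the supplied text randomises, alternates or adjusts for side. With one order in all subjects, the data hold no information from which a side effect could be estimated.

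At stake is how the histology result can be read. Protocol 1.2 names collagen formation as a target of the sub-study, and each volunteer has two excisions to answer that question. The confounding cannot be undone once the samples are taken.

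**Working it through.** The documents give no figure for this point, so there is none to reproduce. The check has three steps.

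**1. What the mean change estimates**

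For subject i and one marker:

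change_i = (BELKYRA + time) + s_i × δ_i + error_i

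Here δ_i is the subject's right-minus-left difference. s_i is +1 if left is sampled first and −1 if right is sampled first. Let δ be the mean of δ_i.

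- Planned design: s_i = +1 for everyone, so E(mean change) = (BELKYRA + time) + δ. The mean side difference enters with coefficient 1. Because s_i never varies, δ cannot be estimated.
- Variation of δ_i around δ averages out over subjects. It widens the interval but does not shift the mean.

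**2. How much it could matter (illustration)**

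From the documents: n = 10 (Protocol 4.1, approximate). Assumed: a paired t-test at two-sided 5%, no true BELKYRA or time effect, and δ expressed in SDs of the paired change.

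- Standard error of the mean change = 1/√10 = 0.316 SD.
- Noncentrality = δ × √10, with 9 degrees of freedom and critical value 2.262.

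| Assumed δ (SD) | Noncentrality | Chance of a significant change |
|---|---|---|
| 0 | 0 | 5% |
| 0.3 | 0.949 | 13.6% |
| 0.5 | 1.581 | 29.3% |
| 0.8 | 2.530 | 61.6% |

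**3. What balancing the side does**

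If k of m completers have left sampled first, the plain mean change carries a bias of δ × (2k − m)/m:

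- 10 of 10 (the plan): δ × 10/10 = 1.0δ
- 7 of 10: δ × 4/10 = 0.4δ
- 6 of 10: δ × 2/10 = 0.2δ
- 5 of 10: 0

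The equally weighted average of the two side-order group means has bias (δ − δ)/2 = 0 at any split with both orders present. Its standard error is (SD/2) × √(1/k + 1/(m − k)). That is 0.316 SD at 5:5 and 0.323 SD at 6:4, so the price of mild imbalance is small.

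Simulation of a 5:5 split with no true effect (200,000 replicates) compared two tests:

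- With side order in the model (8 degrees of freedom), the false-positive rate is 4.9% to 5.0% for δ from 0 to 1 SD.
- An unadjusted paired t-test is unbiased but conservative: 4.3% at δ = 0.25, 2.9% at 0.5 and 0.7% at 1 SD. It counts the side difference as noise.

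**The case against.** The strongest reply is that the harm is hypothetical. Nothing in either document suggests that these four markers differ systematically between mirror-image sites 1.5 cm either side of the midline. The values in the table are assumptions, and at zero the test keeps its nominal 5%. This stands: the point is a design weakness, not a demonstrated bias. That the scheme could not reveal a side difference does not show that one exists.

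A reader might also infer that any left-right difference in tissue is counted as a drug effect. The documents do not support that. Only a difference with the same average direction across subjects shifts the mean change.

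Other replies stand in part:

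- The committed output is descriptive. The SAP says of a test only that "Statistical comparisons from baseline to after final BELKYRA® treatment (based on mean change) may be performed", so the rejection rates describe an analysis that may never be run. The shift in the mean, if any, would be there with or without a test.
- SAP Appendix I and the Biopsy Manual are not in the supplied text and might mention side. Under the order fixed in Protocol 7.1.7, no model in Appendix I could separate side from time point.
- Using the opposite side at the second visit may avoid the first biopsy's scar. The documents do not give this reason, and a balanced order keeps that benefit.
- A single arm without untreated biopsies confounds BELKYRA with time in any case. This is true, and balancing the side does not cure it.

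**Conclusion.** The point holds as a minor, cheaply corrected design weakness. Side and time point are completely confounded, so a systematic right-left difference would be carried at 100% into the mean change, undetectably. Its actual size is unknown and may be zero. The range of 5% to 62% false positives rests on the assumed test, n = 10 and assumed side differences of 0 to 0.8 SD.

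The reach is limited to about 10 volunteers and to an endpoint that is secondary in the protocol and exploratory in the SAP. The primary ALJDS responder rate is untouched. It would go too far to conclude that the histology results are biased, or that balancing the side would make the change attributable to BELKYRA. The documents support neither.

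**What to change.** **Protocol 7.1.7 and the Biopsy Manual.** Assign the side sampled at Visit B1 in a balanced way, alternating or randomised by order of sub-study entry and tracked centrally or within site. Sample the opposite side at Visit B2. Record the side at both visits.

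**SAP 6.2.3.2.** State that side order is in the model, so that the mean change is the equally weighted average of the two side-order group means. This matters because completers may not split evenly. The sub-study is voluntary, and Protocol 4.1 and 6.1.4 do not replace subjects once they have received BELKYRA. The adjustment keeps the estimate unbiased under imbalance and avoids the conservative unadjusted test. List the changes by side order.

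**Cost.** Some administration to track the assignment, which is more than a one-line edit in a multi-centre study, and one degree of freedom (9 to 8). If biopsies have already been taken in the fixed order, those pairs cannot be repaired by analysis, and the report should state the limitation.

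The change removes only the side component. The report should still say that change over time in a single arm cannot be separated from BELKYRA.
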